4.0 Rationale

This protocol describes a post-marketing, observational registry that will evaluate the long-term safety and effectiveness of HUMIRA® as used in routine clinical practice in

adult patients with moderate to severe chronic plaque psoriasis, who are candidates for systemic therapy or phototherapy. This registry is part of a post-marketing commitment from AbbVie to the FDA and European Medicines Agency (EMA).

The participating physicians, with regard to countries and sites, will be representative of the dermatologists who prescribe HUMIRA® for patients with psoriasis in North America and Europe. Similarly, the patients selected for enrollment in the registry will be representative of the population for which HUMIRA® is used to treat psoriasis in the participating countries. The patients will receive commercial HUMIRA® that will be prescribed per their local prescribing information.

[figure not shown]
The data collected in this registry will be complementary to those from the pre-registration studies of HUMIRA® in psoriasis. The management of the patients in this registry will reflect the use of HUMIRA® in current clinical practice. The participating physician is free to determine the appropriate therapy for each patient and make treatment choices as deemed clinically necessary. Patients who consent to participate in the registry, will be followed for up to 10 years, providing important long term safety and effectiveness data on HUMIRA® in Ps patients. A follow-up procedure for patients who discontinue from the registry has been added to the protocol to maximize the safety information collected from all registry patients. The follow-up procedure will be referred to as the direct to Health Care Provider process (HCP) throughout the protocol.

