6.1.3 Patient Follow-up Criteria – HCP Process

Patients who discontinue from the registry before Year 10 will be offered the option to participate in a direct to HCP Process, as applicable per local regulations. In order to participate in the follow-up process, the patient must sign a Patient Authorization for Use/Disclosure of Data form.

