If treatment with HUMIRA® is permanently discontinued for any reason, patients will be encouraged to remain in the registry. If a patient discontinues the registry, the physician will offer the patient participation in the direct to HCP Process, as applicable per local regulations, regardless of HUMIRA® treatment. Patients that have affirmatively

withdrawn their authorization to have their personal health information used or disclosed in connection with the registry will not be asked to continue in the registry or asked to participate in the HCP Process.

For patients who discontinue the registry, physicians will be asked to obtain the patient's signature on a Patient Authorization for Use/Disclosure of Data form for the completion of a simplified Healthcare Provider (HCP) questionnaire on an annual basis, as applicable per local regulations. The first data collection period will capture data from the date of the patient's discontinuation visit or last contact in the registry through the completion of the first annual HCP questionnaire for the patient. The questionnaire focuses on the collection of surgeries, hospitalizations, deaths, and the events listed as AEs of Special Interest (Table 2), AEs of Special Interest that lead to permanent discontinuation of HUMIRA®, and psoriasis related medication use since registry discontinuation. The questionnaire may be completed by the registry physician or the patient's current HCP (if they are no longer under the care of a registry physician). Any other SAEs experienced should be reported according to standard spontaneous reporting procedures, and they are not subject to the requirements of this protocol.

Effectiveness measures will not be collected from patients participating in direct to HCP Process.

All patients that are unreachable after three consecutive documented attempts to contact the patient via phone, email, or certified letter, will be considered lost to follow-up.

AbbVie will take reasonable actions to ascertain vital status at the end of the patient's 10-year observational period. AbbVie will make every effort to work through investigational sites to match patients lost to follow-up against the National Death Index (NDI) in the US, national/regional cancer registries and vital registries as available in other countries and as allowed per local regulations.

The registry procedures to be conducted in the registry are outlined in the schematic presented in Table 1.

[figure not shown]

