6.6 Withdrawal of Patients from Registry

A patient may withdraw from the registry at any time without prejudice. If the physician, for any reason, decides it is in the best interest of the patient to permanently discontinue HUMIRA[®], treatment should be stopped but the patient should be encouraged to continue in the registry as outlined in Section 6.0. If a patient withdraws or is lost to follow-up,

such should be noted, along with the reason for withdrawal on the Study Completion eCRF.

Patients who discontinue from the registry for any reason other than withdrawn consent, will be contacted to determine interest in participation in the direct to HCP Process, as applicable per local regulations.

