7.1.3 Serious Adverse Events

If an AE (not limited to AEs of Special Interest) meets any of the following criteria, it is to be reported to AbbVie as a SAE within 24 hours of the site being made aware of the event.

Death of Patient	An event that results in the death of a patient.
Life-Threatening	An event that, in the opinion of the investigator, would have resulted in immediate fatality if medical intervention had not been taken. This does not include an event that would have been fatal if it had occurred in a more severe form.
Hospitalization	An event that results in an admission to the hospital for any length of time. This does not include an emergency room visit or admission to an outpatient facility.
Prolongation of Hospitalization	An event that occurs while the patient is hospitalized and prolongs the patient's hospital stay.
Congenital Anomaly	An anomaly detected at or after birth, or any anomaly that results in fetal loss.

Obvie HUMIRA® (adalimumab) P10-023 Protocol Amendment 3 Psoriasis HUMIRA® Registry

Persistent or **Significant** Disability/Incapacity An event that results in a condition that substantially interferes with the activities of daily living of a patient. Disability is not intended to include experiences of relatively minor medical significance such as headache, nausea, vomiting, diarrhea, influenza, and accidental trauma (e.g., sprained ankle).

Important Medical Event Requiring Medical or Surgical Intervention to Prevent Serious Outcome

An important medical event that may not be immediately life-threatening or result in death or hospitalization, but based on medical judgment may jeopardize the patient and may require medical or surgical intervention to prevent any of the outcomes listed above (i.e., death of patient, life-threatening, hospitalization, prolongation of hospitalization, congenital anomaly, or persistent or significant disability/incapacity). Examples of such events include allergic bronchospasm requiring intensive treatment in an emergency room or at home, blood dyscrasias or convulsions that do not result in inpatient hospitalization, or the development of drug dependency or drug abuse.

Spontaneous Abortion

Miscarriage experienced by patient.

Elective Abortion

Elective abortion performed on patient.

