8.0 Ethics and Quality

Prior to any registry-related data being collected, the informed consent statement will be reviewed and signed and dated by the patient and the person who administered the informed consent. A copy of the signed informed consent form will be given to the patient and the original will be placed in the patient's medical record. A patient informed consent template will be provided to the registry physician.

If a patient is willing to participate in the HCP process, a copy of the signed Patient Authorization for Use/Disclosure of Data form will be obtained prior to the participation.

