10.3.1 Analysis of Observational AEs

The number and percent of patients experiencing SAEs, AEs of Special Interest and AEs that lead to permanent discontinuation of HUMIRA® during the registry, regardless of whether the AEs are reported during or after the HUMIRA® treatment, will be tabulated by body system and Medical Dictionary for Drug Regulatory Activities (MedDRA) preferred term. Rates (event per 100 patient-year of observation) of SAEs and AEs of Special Interest and the 95% confidence interval will be provided. The analysis will be performed using data from first day in the registry to the date of last contact for the All Treated Patient Population. The last contact date is defined as the last date of registry or direct to HCP process participation, whichever occurs later.

Standardized incidence ratios (SIRs) will be used to compare the rates of events in this registry to the general population.

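### Where a leaver signs the HCP authorization some time after exit, the interval up to signature is immortal time and lowers death and fatal-event rates in the 10.3.1 Observational analysis

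*Protocol*

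**What the plan says.** Four rules of the protocol act together.

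- **Entry by signature.** Section 6.1.3: "In order to participate in the follow-up process, the patient must sign a Patient Authorization for Use/Disclosure of Data form". Section 8.0 adds that "a copy of the signed Patient Authorization for Use/Disclosure of Data form will be obtained prior to the participation".
- **Timing of the offer.** Section 6.6 says that patients who discontinue for reasons other than withdrawn consent "will be contacted to determine interest in participation in the direct to HCP Process". Section 6.5 has the physician make the offer when a patient discontinues. Neither gives a deadline for the signature.
- **Back-fill.** Section 6.5: "The first data collection period will capture data from the date of the patient's discontinuation visit or last contact in the registry". Exit can therefore be dated by a last contact, without any exit visit.
- **Observation time.** Section 10.3.1: "Rates (event per 100 patient-year of observation) of SAEs and AEs of Special Interest and the 95% confidence interval will be provided". The analysis runs from the first registry day to last contact, and "The last contact date is defined as the last date of registry or direct to HCP process participation, whichever occurs later".

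Death is a counted event: the first SAE criterion in Section 7.1.3 is "An event that results in the death of a patient". Section 4.0 also notes: "A follow-up procedure for patients who discontinue from the registry has been added to the protocol". It gives no date for that addition.

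**The concern.** Suppose a patient leaves the registry, is approached some months later and signs. The months between exit and signature are back-filled and enter the denominator. Now suppose the same patient dies in those months. No signature is ever given, last contact stays at registry exit, and neither the death nor the time after exit enters the rate. The interval is counted only for people known to have survived it, so it adds person-time in which no death could have been recorded. That is immortal time, and for death it can act only downward, in favour of the drug.

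The 10.3.1 analysis is the one that uses all follow-up, and it carries the SIRs. Long-term safety is the primary objective, so a one-directional error in its fatal-event rates deserves correction even if it is small.

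**Working it through.** **Is the interval in the denominator?** By 10.3.1 a signer's observation is continuous from the first registry day to the last HCP date, so it includes the interval. Section 10.2 words the end of observation differently, by reference to the end-of-registry in Section 12.0. The interval after exit lies inside a signer's observation on that reading too. No rule starts HCP time at the signature.

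**Formula.** Let *h* be the true death rate, *T* the counted patient-years (PY), and *G* the PY between exit and signature contributed by signers. No death can be counted in *G*, so counted deaths are h(T - G) and the reported rate is h(T - G)/T. The relative shortfall is G/T, and it barely depends on *h*.

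**The plan's own figure.** Section 10.6: 6,000 patients x 10 years x (1 - 0.40) = 36,000 PY, which reproduces. The 21,500 PY requirement for lymphoma is not in question here.

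**Missing inputs.** The protocol gives neither the length of the gap nor the share of leavers who sign. Both are assumptions below.

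*Simple arithmetic.* Take T = 36,000 and let 25% of all 6,000 patients sign late, so G = 0.25 x 6,000 x gap:

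| Gap | G (PY) | G/T |
|---|---|---|
| 0 | 0 | 0% |
| 1 month | 125 | 0.3% |
| 3 months | 375 | 1.0% |
| 1 year | 1,500 | 4.2% |
| 2 years | 3,000 | 8.3% |

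At a gap of 1 year, a share of 10% gives 600/36,000 = 1.7%, and a share of 50% gives 3,000/36,000 = 8.3%.

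*Simulation with HCP time added to registry time.* A constant exit rate is chosen so that mean registry time is 6 of 10 years, which means about 68% leave before year 10. Half of the leavers sign, if alive, after an exponential gap, and are then followed to year 10. The death rate is constant at 1 per 100 PY. Per 6,000 patients:

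| Mean gap | G (PY) | T (PY, about) | Overall death rate too low by | Post-exit rate too low by |
|---|---|---|---|---|
| 3 months | 470 | 45,800 | 1.0% | 4% |
| 6 months | 900 | 45,800 | 2.0% | 8% |
| 12 months | 1,680 | 45,700 | 3.7% | 15% |
| 24 months | 2,690 | 45,200 | 6.0% | 25% |

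*Second simulation, different exit pattern.* Here 60% leave, exit is uniform over 0.25 to 10 years, half of the leavers sign, and the gap is fixed. Against a true 1.00 per 100 PY, the overall rate is 1.00, 0.99, 0.97 and 0.94 for gaps of 0, 3 months, 1 year and 2 years. Within HCP time alone it is 1.00, 0.95, 0.81 and 0.65. Starting person-time at signature returns every figure to 1.00 within simulation error.

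**Do other provisions bring the missing deaths back?** Section 6.5 plans matching to the National Death Index and other registries, but only for patients lost to follow-up and as local rules allow. Section 7.4 keeps reporting open for at least 70 days after the last registry dose, so some early deaths may reach the sponsor. Deaths found either way fall after the last-contact date of 10.3.1, and nothing in that section brings them into the rate.

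**The case against.** The best case against the point is that a gap need not exist. Table 1 has a premature-discontinuation visit, and Sections 6.4 and 9.0 call for a medical assessment at exit. The form can be signed there, and then the bias is zero. This stands, so a reader who infers that the planned rates are certain to be too low goes further than the protocol allows. It does not dispose of the point: Section 6.6 permits later contact, Section 6.5 permits exit dated by last contact, and no deadline closes the gap.

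Three other strong readings are also unsupported:

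- *All malignancy rates and SIRs are distorted.* Non-fatal diagnoses in the gap, lymphoma and skin cancer included, can be reported by the physician or current provider through the back-fill. Only cases that were fatal, or that prevented signature, are lost.
- *Only 10.3.4 is safe.* Treatment-emergent rates are touched only where HUMIRA continues after exit.
- *Gaps are long because the HCP process was added later.* Section 4.0 gives no date, and nothing says earlier leavers were approached. Nor does any section show that sicker patients leave more often; the simulations assume a constant death rate.

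It is also fair to say that the effect is small beside sampling error. At the assumed 1 death per 100 PY, 36,000 PY gives 360 deaths and a 95% interval of about +/-10% (1.96/sqrt(360) = 0.103). That limits the importance of the point. But the bias has one direction, does not shrink as PY accumulate, and can be removed by wording.

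**Conclusion.** The point holds in a conditional and limited form. For patients who sign after exit, Sections 6.5 and 10.3.1 together count immortal time, and rates of death and fatal events in the Observational analysis are biased downward. Fatal or incapacitating cases within other rates and SIRs share the bias.

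The size cannot be read from the protocol. It is nil with signature at the discontinuation visit. If half of leavers sign, the overall rate is about 1-2% too low for mean gaps of 3-6 months and about 4-6% for 1-2 years. The 4-25% shortfall in post-exit time should not be taken as the effect on a planned result, because the protocol plans no separate HCP-phase rate. The analysis in 10.3.4 is unaffected, but it drops all HCP follow-up and so does not correct 10.3.1.

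This is a cheap improvement worth making. It does not invalidate the registry's safety results.

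**What to change.** In Section 10.3.1, for death and fatal events, end registry person-time at the discontinuation visit or last registry contact. Start HCP events and person-time at the date of the signed authorization (delayed entry). State that fatal events are placed by date of death, so that the event and the person-time follow one rule.

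Keep the back-filled gap for non-fatal events in the main analysis; removing it there would discard validly observed events. Add a sensitivity analysis that applies delayed entry to all events and to the SIRs. List deaths known to have occurred in the gap from any source, including registry matching and reporting after the last dose.

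Cost: analysis wording, no new visits, and a small loss of person-time for fatal-event rates (about 1-6% under the assumptions above). The authorization date must be available. Section 8.0 says only that a copy of the signed form is obtained, so the date may have to be taken from the form if it is not already in the database.

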6.5.1 Inclusion/Exclusion

Patients will be screened to ensure they meet all inclusion criteria and do not meet the exclusion criteria prior to enrollment.

6.5.2 Demographics

Once the physician has determined that the patient is eligible for inclusion, and the patient has agreed to be included in the observational registry, the patient's demographic data, including date of birth, gender, race, ethnicity, and disease status will be recorded on the eCRFs at the Enrollment Visit.

6.5.3 Medical History

[figure not shown]
The physician will determine the patient's current health status and obtain a complete medical history including history of tobacco, alcohol and drug abuse at the enrollment visit.

After consent is obtained, patients will be asked to provide retrospective SAEs, AEs of Special Interest, and exposure to HUMIRA® data from the first dose of commercial HUMIRA®.

Patients rolling over from a prior HUMIRA® clinical trial will be asked to provide medical history only for previously unreported conditions and/or conditions not requested to be reported in the original study of participation.

6.5.4 Prior and Concomitant Medications

All prior and ongoing systemic therapy, biologic agent, and phototherapy to treat psoriasis since diagnosis should be documented. Prior systemic therapy for non-psoriasis medical conditions will be recorded for the prior 12 months. For all prior psoriasis therapies,

Psoriasis HUMIRA® Registry

information on dosing, response to treatment, the year of last administration, length of time on the medication, and reason for stopping the psoriasis medication will be collected in the source documents and appropriate eCRF pages.

[figure not shown]
Any changes to ongoing psoriasis medications and new concomitant psoriasis medications should be recorded throughout the course of the registry. Medications used to treat AEs of Special Interest and/or SAEs will be recorded at the time of the event.

In addition, for patients age 30 with a reported malignancy adverse event, prior exposure to, or current use of, antineoplastics, or other drugs which have a risk of malignancy as stated in their label and other relevant dosing information to estimate total exposure will be collected in the source documents and appropriate eCRF pages. At the time of the reported malignancy adverse event, sites will be asked if any of the prior and concomitant medications contributed to the event. Any medications used prior to the registry will be captured on the appropriate eCRF. Information on the reason for use, date(s) of administration including start and end dates, highest maintained dose, dosage information including dose, route and frequency, and reason for stopping the medication will be collected in the source documents and appropriate eCRF pages.

Since this is an observational registry, the patient will be treated in accordance with the physician's usual and customary medical practice.

The administration of anakinra (Kineret[®]), abatacept (Orencia[®]) or other biologic agents may not be given concurrently while participating in the registry. Please refer to your local product label for the use of live vaccines while a patient is on HUMIRA[®].

The AbbVie Study-Designated Physician (SDP) should be contacted if there any questions regarding prior or concomitant medications.

6.5.5 Physician's Global Assessment and Patient Reported Outcome Measurements

When applicable, information about the effectiveness of HUMIRA® therapy will be provided by the physicians and the patients. The Physician's Global Assessment (Appendix C) will be collected to assess the effectiveness of therapy at all registry visits at all sites. Effectiveness of therapy provided by the patient will be collected at US sites only utilizing patient reported outcomes (PROs) beginning at the enrollment visit and subsequently as outlined in Table 1. Effectiveness measures will be collected for patients participating in the registry regardless of HUMIRA® treatment. However effectiveness measures will not be collected as part of the HCP process. The PROs to be utilized include: Dermatology Life Quality Index (DLQI) (Appendix D), Patient Health Questionnaire PHQ-9 For Depression (PHQ-9) (Appendix E), Healthcare Resource Utilization (Unscheduled Outpatient Visits, Emergency Room Visits and Hospitalizations Questionnaire) (Appendix F), Work Productivity and Activity Impairment Questionnaire: Specific Health Problem V2.0 (WPAI:SHP) (Appendix G), Rosenberg Self-Esteem Scale (Appendix H, Census Socio-Demographic Questionnaire (Appendix I), Medical Outcomes (MOS)-Social Activities Scale (Appendix J), Psoriasis Impact and Experience (Appendix K), Illness Cognition Questionnaire (Appendix L), Insurance Status (Appendix M), and Patient Global Assessment (Appendix N).

6.5.6 Product Supply

HUMIRA® will be obtained through commercially available medication. AbbVie will not provide the medication for this registry.

6.6 Withdrawal of Patients from Registry

A patient may withdraw from the registry at any time without prejudice. If the physician, for any reason, decides it is in the best interest of the patient to permanently discontinue HUMIRA[®], treatment should be stopped but the patient should be encouraged to continue in the registry as outlined in Section 6.0. If a patient withdraws or is lost to follow-up,

such should be noted, along with the reason for withdrawal on the Study Completion eCRF.

Patients who discontinue from the registry for any reason other than withdrawn consent, will be contacted to determine interest in participation in the direct to HCP Process, as applicable per local regulations.

